2.5 Feasibility

Given that our laboratory has already developed the prototype of the iMBT, it is anticipated that this trial will be completed within a 2-year period, with approximately 70% of participants retained. This is in line with similar e-psychotherapy studies where one meta-analysis reported an average of 23% dropout.

References

1. SchulzKF, AltmanDC, MoherD. CONSORT 2010 Statement: Updated guidelines for reporting parallel group randomised trials. *Ital J Public Health*. 2010. doi:10.4178/epih/e2014029
2. SheehanDV., LecrubierY, SheehanKH, et al. The Mini-International Neuropsychiatric Interview (M.I.N.I.): The development and validation of a structured diagnostic psychiatric interview for DSM-IV and ICD-10. In: *Journal of Clinical Psychiatry*. ; 1998.
3. MakWWS, TongACY, YipSYC, et al. Efficacy and moderation of mobile app–Based programs for mindfulness-Based training, self-Compassion training, and cognitive behavioral psychoeducation on mental health: Randomized controlled noninferiority trial. *J Med Internet Res*. 2018. doi:10.2196/mental.8597
4. StoneAB. Mindfulness-Based Cognitive Therapy for Depression: A New Approach to Preventing Relapse. *Psychiatr Serv*. 2005. doi:10.1176/appi.ps.56.9.1165
5. SpijkermanMPJ, PotsWTM, BohlmeijerET. Effectiveness of online mindfulness-based interventions in improving mental health: A review and meta-analysis of randomised controlled trials. *Clin Psychol Rev*. 2016. doi:10.1016/j.cpr.2016.03.009
6. JacobsonNS, TruaxP. Clinical Significance: A Statistical Approach to Defining Meaningful Change in Psychotherapy Research. *J Consult Clin Psychol*. 1991. doi:10.1037/0022-006X.59.1.12
7. ByrneBM. *Structural Equation Modeling with AMOS: Basic Concepts, Applications, and Programming, Second Edition.*; 2013. doi:10.4324/9780203805534
8. DuncanTE. *An Introduction to Latent Variable Growth Curve Modeling.*; 2013. doi:10.4324/9780203879962
9. MacKinnonDP, LockwoodCM, WilliamsJ. Confidence limits for the indirect effect: Distribution of the product and resampling methods. *Multivariate Behav Res*. 2004. doi:10.1207/s15327906mbr3901_4
10. HuLT, BentlerPM. Cutoff criteria for fit indexes in covariance structure analysis: Conventional criteria versus new alternatives. *Struct Equ Model*. 1999. doi:10.1080/10705519909540118

7. Working Schedule

- | | | |
|---------------------------------|----------------------|--------------|
| a) Start Date: | June 30, 2020 | (DD/MM/YYYY) |

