1.3 Aims and hypotheses

The research goals of this randomized controlled trial are to determine the feasibility and the mechanism of change of iMBT that has been developed using the Acceptance Checklist for Clinical Effectiveness Pilot Trials (ACCEPT) framework³⁵.

The primary research question is as follows:

- What is the effectiveness of the iMBT in relation to improvements on depressive symptoms among people with clinical depression, relative to a usual care control after the intervention and in 3-month follow-up?

Secondary questions include the following:

- Which facet(s) of mindfulness (i.e., observe, describe, act with awareness, non-react and non-judgement) improved during the intervention?
- How does the growth trajectory of different facets of mindfulness relate to the improvement of well-being and reduction of ill-being?

We hypothesize that:

- H1 Participants in iMBT group will have greater reduction in depressive symptoms and increase in all facets of mindfulness and mental well-being, than the usual care group at post-intervention, and 3-month follow-up.
- H2 Using latent growth analysis, the intraindividual growth trajectory of the monitor and acceptance facets of mindfulness would mediate the effect of iMBT on the intraindividual changes in depressive symptoms.
- H3 Using multi-group analysis, in accord with Acceptance and Monitor theory, the relationship between the growth trajectory of monitor facets of mindfulness and the growth trajectory of depressive symptoms will be moderated by the level of acceptance. People with greater acceptance of inner experience will benefit more from the change of monitor facets of mindfulness in iMBT.

References

1. FerrariAJ, SomervilleAJ, BaxterAJ, et al. Global variation in the prevalence and incidence of major depressive disorder: A systematic review of the epidemiological literature. *Psychol Med*. 2013. doi:10.1017/S0033291712001511
2. LiuQ, HeH, YangJ, FengX, ZhaoF, LyuJ. Changes in the global burden of depression from 1990 to 2017: Findings from the Global Burden of Disease study. *J Psychiatr Res*. 2019. doi:10.1016/j.jpsychires.2019.08.002
3. PatelV, ChisholmD, ParikhR, et al. Addressing the burden of mental, neurological, and substance use disorders: Key messages from Disease Control Priorities, 3rd edition. *Lancet*. 2016. doi:10.1016/S0140-6736(15)00390-6

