2.1 Trial design, Procedure and Study Flow

A two-armed parallel RCT following CONSORT statement¹ will be conducted to examine the efficacy of an Internet-based mindfulness-based training (iMBT) to a treatment-as-usual control group (TAU). Intervention (iMBT) will be delivered over a 6-week period via an internet e-learning mental health platform.

All participants who are interested to join this research will be provided with an electronic informed consent form, and online screening. The online screening included a self-assessment of depressive symptoms using PHQ-9 as well as items that assessed the inclusion and exclusion criteria.

Participants will be included if they are: (1) aged over 18, (2) have access to computer and mobile phone, (3) scored > 9 on PHQ-9, administered via telephone by trained interviewers, and (4) have ability to read and type Chinese. Exclusion criteria includes (1) self-reported presence of psychosis or bipolar disorder, post-traumatic stress disorder, drug or alcohol dependence, current use of antipsychotic medications, (2) self-reported frequent suicidal ideation (more than half of the days in the past two weeks), (3) completion of an online mental health program/research for depression in the past 3 months.

Any excluded applicants will receive contact information on community mental health services. Following telephone assessment, eligible participants will be randomized to either iMBT or TAU by block randomization with block number of 6 with allocation ratio of 1:1.

Participants will be assessed at the following time points: (1) before intervention (T0), (2) 2,4 weeks since the commencement of group (T1,2), (3) 6 weeks after (i.e., when the intervention ends) (T3), (4) at 3-month follow-up (T4). Participants in the TAU will have the assessment according to specific times as the iMBT group (i.e. weeks since commencement of group) (see Figure 1).

[figure not shown]

Figure 1 CONSORT flow diagram

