2.3 Power Calculation and Sample Size

Based on past research⁵, we expected a small to medium ($f = 0.11$) difference between the iMBT and the TAU control group. Thus, using G * Power software (version 3.1.9.2), a sample size of 116 will be needed to detect superiority of the intervention groups over the TAU control group with 80% power.

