2.4 Analytical procedure

2.4.1 Efficacy analyses of iMBT on Depressive symptoms, Mindfulness, and Mental Well-being

Significance testing of baseline group equivalence will be conducted using Analysis of variance (ANOVA) and chi square test if the variables consisted of nominal data.

To investigate the efficacy of iMBT, intention-to-treat (ITT) linear mixed models using restricted maximum likelihood (REML) estimation will be conducted for each outcome measure.

Fixed factors of time, group, and time*group will be entered in each model. Within-group effect size will be computed for pre(T0)-to-post(T3), and pre(T0) to follow-up(T4) changes on each outcome measures, and between-group effect sizes (Hedge's g) will be computed at post(T3) and follow-up(T4). Reliable change scores were calculated⁶ between pre(T0)and post(T3)-intervention, as well as between pre(T0)and follow-up(T4) for the PHQ-9, to determine rates of clinically reliable improvement and deterioration. All analyses will be performed in SPSS version 24.

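### Section 2.3 states 80% power for 116 participants with no allowance for loss, while Section 2.5 expects about 70% of participants to be retained

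*Protocol*

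**What the plan says.** Section 2.3 bases the trial's size on one calculation. It takes the effect from past research, "we expected a small to medium ($f = 0.11$) difference between the iMBT and the TAU control group", names G*Power as the software, and concludes that "a sample size of 116 will be needed to detect superiority of the intervention groups over the TAU control group with 80% power". It does not mention loss to follow-up, and it does not separate the number randomised from the number analysed.

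Section 2.5 gives the expected retention: "it is anticipated that this trial will be completed within a 2-year period, with approximately 70% of participants retained". It calls this in line with "similar e-psychotherapy studies where one meta-analysis reported an average of 23% dropout".

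The efficacy analysis in Section 2.4.1 is a mixed model: "intention-to-treat (ITT) linear mixed models using restricted maximum likelihood (REML) estimation will be conducted for each outcome measure". The primary question in Section 1.3 is about depressive symptoms "relative to a usual care control after the intervention and in 3-month follow-up". Section 2.1 sets 1:1 allocation but states no number to be randomised.

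**The concern.** G*Power's repeated-measures routines compute power for complete data, so a bare G*Power figure contains no loss unless the author adds it, and Section 2.3 does not say that anything was added. If 116 is the number randomised, the 80% describes a trial with more complete data than Section 2.5 expects.

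This matters because 80% power is the only justification given for the size of the trial. The primary comparison is made at the end of treatment and at 3 months, the last two assessments, where cumulative loss would normally be greatest. A reader also cannot tell which trial is planned: about 81 retained from 116 randomised, or about 166 randomised to retain 116.

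**Working it through.** **Inputs from the protocol.** f = 0.11, N = 116, power 80% (Section 2.3); 1:1 allocation (Section 2.1); 70% retained and 23% dropout elsewhere (Section 2.5); ITT mixed model (Section 2.4.1).

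**Inputs assumed, because Section 2.3 omits them.** Within-between interaction F test, two-sided alpha 0.05, m = 4 measurements, correlation r = 0.5.

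**Step 1: reproduce 116.** Noncentrality λ = f²·N·m/(1 − r), with df (m − 1) and (N − 2)(m − 1).
- N = 116: λ = 0.0121 × 116 × 4/0.5 = 11.23, df 3 and 342, power 0.808.
- Smallest even N reaching 0.80: 114.

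So 116 is reproduced to within 2 with no allowance for loss. The between-group main effect, λ = f²·N·m/(1 + (m − 1)r), cannot give 116 at alpha 0.05: it needs at least 132 with up to five measurements and r ≥ 0, and 652 with one measurement.

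**Step 2: expected retention.** 0.70 × 116 = 81.2. At 23% loss, 0.77 × 116 = 89.3.

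**Step 3: lower reference, completers only.** N = 81 gives 0.64 and N = 89 gives 0.68. This is not the planned analysis, which keeps partial data.

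**Step 4: the planned mixed model, 116 randomised.** Compound symmetry and monotone loss are assumed. With p_q the share of participants observed up to visit q, the information per participant is I = Σ p_q V_q⁻¹, and C = I⁻¹. For the contrasts from baseline, d = Lδ, λ = d′[L C L′·4/N]⁻¹d. The effect is scaled so that complete data give λ = 11.23. Early loss means all loss after T0; late loss means all loss before the last visit.

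| Loss timing | 70%, linear effect | 70%, early step effect | 77%, linear effect | 77%, early step effect |
|---|---|---|---|---|
| Early | 0.68 | 0.70 | 0.71 | 0.73 |
| Even | 0.69 | 0.76 | 0.73 | 0.77 |
| Late | 0.72 | 0.79 | 0.74 | 0.80 |

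All six results at 70% are below 0.80. An effect seen only at the last visit would give about 0.65 at 70%. For the patterns in the table, the effect detectable with 80% power moves from f = 0.109 with complete data to 0.111–0.126 at 70% and 0.110–0.121 at 77%.

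**Step 5: other unstated inputs, 116 randomised, 70% retained, same six patterns.**
- Settings tuned to return exactly 116 without loss (m = 2 to 5, r about 0.65 down to 0.42): about 0.67 to 0.80.
- m = 5, r = 0.5 (100 needed; 0.86 at 116 with complete data): 0.74 to 0.86.
- m = 5, r = 0.60; m = 4, r = 0.65; or m = 3, r = 0.70 (each needs 82, and 82/0.70 = 117): 0.82 to 0.93. Here 116 would already contain an allowance.

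**Step 6: if 116 is the analysable number.** 116/0.70 = 165.7, so about 166 randomised (116/0.77 = 150.6, about 151, at 23% loss).

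**The case against.** The case against is substantial. No outright contradiction is shown: Section 2.3 speaks of a sample size, not of a number randomised, and the two sections agree if 116 is the analysable number or already includes an allowance. The CONSORT diagram (Figure 1) is not shown and may carry the number randomised. Section 2.5 does not define retention or name a visit, so it could mean completing the programme; ITT outcome data need not then be lost at that rate. The size of any shortfall depends on inputs that nobody outside the sponsor knows. Five measurements is a natural choice, since Section 2.1 lists T0 to T4, and with r = 0.5 the range reaches 0.86.

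All of this stands and limits what can be claimed. A reader might infer that the 80% holds only if nobody is lost. The documents do not support that: 114 already suffices under the reproducing inputs, the mixed model uses partial data, and some inputs keep power above 0.80 at 70% retention. Nor should the completers-only 0.64 be read as the trial's power.

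The objection does not supply the missing link. Section 2.3 claims no allowance, and the reader cannot tell which interpretation applies.

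**Conclusion.** The point holds in limited form and should be fixed. Read plainly, the 80% in Section 2.3 assumes a retention that Section 2.5 does not expect. Under inputs that reproduce 116 without an allowance (four measurements, r = 0.5, alpha 0.05, interaction test), the planned analysis has power of about 0.68 to 0.79 at 70% retention and about 0.71 to 0.80 at 23% loss, depending on when loss occurs and the shape of the effect. These figures also assume compound symmetry, monotone loss and 116 as the number randomised.

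The calculation itself is not shown to be wrong: 116 reproduces to within 2. A reader might also infer that the trial is underpowered and must recruit 166. That does not follow, since 166 applies only if 116 is meant as the analysable number. Confidence is medium, because the deciding inputs are not stated.

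**What to change.** In Section 2.3, replace the 80% with the power, or the detectable effect, of the planned mixed model for 116 randomised at the 70% retention given in Section 2.5. Use the sponsor's own G*Power inputs, and state them: test, alpha, number of measurements, correlation, and the assumed timing of loss.

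If 116 is the analysable number, say so and give the number to be randomised (about 166 at 70% retention). If 116 is randomised and already includes an allowance, say so and give the analysable number (about 81). In either case, say whether retention means outcome data or programme adherence.

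The change is to the wording of Section 2.3 plus one rerun of the calculation, and it asks for no increase in enrolment. The cost is that the stated power may become somewhat less favourable. If 116 was always the analysable number, a recruitment target that is now implicit becomes explicit.
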